
Procedures/ Methods:
	
Subjects in the initial pilot period (Part 1) and validation testing (Part 2) will undergo up to 45 minutes of ultrasound scanning, including up to 8 test scans on the Vscan Access R2 Ultrasound System with Assisted FHR (research device) and a conventional commercially available ultrasound device. Subjects will also undergo routine commercially available noninvasive FHR monitoring as a reference. All procedures will be conducted at a Sponsor, GE Healthcare (GEHC), facility. All members of the study staff will be qualified based on experience and trained prior to participation.
 
The study population will consist of asymptomatic women ages 18 or older in the second (2nd) and third (3rd) trimesters of pregnancy. Users will be instructed to use the VScan Access R2 device to take a 3 second video of the volunteer, which will result in a calculated fetal heart rate measurement from the monitor. Volunteers will also undergo routine commercially available FHR monitoring using the current standard of care.
 
The first session (Part 1) will be a run-in session, in which the parameters and procedures will be a replica of the study but these results will not count towards the documented results. There will be four (4) sessions following this run-in session (Part 2). Each of these sessions will be approximately 3-4 hours in length over a period of 1-2 weeks.
 
In each session, there will be 1-2 users and 3 volunteers. The users will be instructed to take as many measurements as possible during the allotted time. Finalization of the procedure to calculate accuracy is to be determined based on the run-in procedures executed in Part 1. The specific procedures for the measurement of accuracy which will be used for validation will be performed by the team during Part 1 of the study.

Objectives:
	
Data from Part 1 and Part 2 may be pooled or analyzed as separate subgroups, as determined necessary by the sponsor.
 
The primary objective is to validate the accuracy of the VScan Access R2 ultrasound assisted FHR measurement compared to the reference standard in a pregnant population.
 
The exploratory objective is to collect usability data for further user experience optimization.
 
The safety objective is to collect safety information, including type and number of AEs, SAEs, and other device issues.

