3.3 Summary of Study Design

This is a Clinical, pre-market open label, non-randomized, prospective, single-site, non-blinded, research study, that will enroll from the accessible adult (aged >18 years) female population in the 2nd and 3rd trimesters of pregnancy. The study will be conducted in two stages, beginning with a run-in study (Part 1), followed by a clinical study (Part 2). The results of the run-in pilot study will not be included in the results and data analysis; rather, Part 1 of this study will be used to test procedures and determine any experimental factors that have yet to be defined. The study will be conducted at a GE-operated facility. The study is expected to last approximately 6 weeks. The study is not statistically powered for any measure, and is intended to evaluate procedural accuracy of the Vscan Access R2 Ultrasound System Assisted FHR versus use of a conventional FHR monitor (reference): GE Corometrics* 170 Series Fetal Monitor.

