5. STUDY PROCEDURES

5.6 Study Parts

The study will be conducted in two parts, including a initial pilot run-in period (Part 1) and testing period (Part 2), as described in Table 1. Patients in both parts of the study will undergo the same procedure and have a similar experience in the study; however, results will not be collected or recorded for analysis from Part 1 of the study

Table 1 - Description of Study Parts

Study Part	Maximum enrollment	Operator Experience Level	Description
Part 1	5	Any experience level	Pilot for determining
Part 2	15	Approx. 4 Novice and 1 Experienced	Scanning with fixed parameters

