10.8 Statistical Analysis

No statistical hypothesis testing is prospectively planned. Gestational age/number and other variables or subgroups determined necessary by the Sponsor, at its discretion, will be summarized as tables and listings, which may include appropriate descriptive statistics when applicable. Subject disposition and number of image sets collected will be summarized in the final report.

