10.8.1 Interim Analysis

No interim analyses are intended to be conducted as part of this study. The Sponsor may access the study data at any time during the study, as necessary for engineering purposes.

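### The synopsis lets the sponsor pool run-in (Part 1) data with Part 2, three other statements exclude Part 1, and 10.8 does not say which rule governs the accuracy estimate

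*Combined protocol and SAP*

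**What the plan says.** One statement permits pooling. It is in the synopsis, Objectives row: "Data from Part 1 and Part 2 may be pooled or analyzed as separate subgroups, as determined necessary by the sponsor".

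Three statements exclude Part 1:

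- Synopsis, Procedures/Methods row, on the run-in session: "these results will not count towards the documented results".
- Section 3.3: "The results of the run-in pilot study will not be included in the results and data analysis".
- Section 5.6: "results will not be collected or recorded for analysis from Part 1 of the study".

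Two statements give Part 1 a role in setting the method. The synopsis Procedures row says: "Finalization of the procedure to calculate accuracy is to be determined based on the run-in procedures executed in Part 1". Section 3.3 says: "Part 1 of this study will be used to test procedures and determine any experimental factors that have yet to be defined".

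Section 10.8 mentions neither part, no pooling rule and no analysis set. On what will be summarised, it says that "other variables or subgroups determined necessary by the Sponsor, at its discretion, will be summarized as tables and listings". Section 10.8.1 plans no interim analysis but adds: "The Sponsor may access the study data at any time during the study, as necessary for engineering purposes".

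**The concern.** The primary objective (3.1.1) is to validate the accuracy of the assisted FHR measurement against the reference. A validation estimate should come from data that played no part in choosing how accuracy is obtained or calculated. The pooling sentence allows the opposite: run-in readings, taken while the procedure was still open, could be counted as validation readings.

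The permission is also unconditional. It does not say what would make pooling necessary, or when the decision must be taken. The study is open label at a sponsor facility and 10.8.1 allows the sponsor access to the data for engineering purposes during the study. The choice between a pooled and a Part 2-only estimate could therefore be made after both have been seen.

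A reader of the final report could not tell from the plan which subjects the accuracy figures were meant to describe. Section 12.6.1 lists regulatory claims among the possible uses of the de-identified data, so this matters beyond the engineering team.

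**Working it through.** **1. The statements side by side.**

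| Place | Part 1 in the analysis? |
|---|---|
| Synopsis, Objectives | Yes, if the sponsor so decides |
| Synopsis, Procedures/Methods | No |
| Section 3.3 | No |
| Section 5.6 | No; not collected or recorded for analysis |
| Sections 10.6 to 10.9 | Silent |

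The synopsis therefore conflicts with itself as well as with the body. The pooling sentence is not limited to safety or usability data, and it stands directly before the primary accuracy objective. Reading it as confined to other data is not supported by its wording.

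**2. The plan's own count.** Section 10.7 gives up to 5 subjects in Part 1 and 20 in Part 2: 5 + 20 = 25, which reproduces the stated maximum. Table 1 caps Part 2 at 15 instead, giving 5 + 15 = 20. The synopsis plans one run-in session and four further sessions. With 3 volunteers in each, including the run-in, that is 3 + 12 = 15.

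**3. Weight of Part 1 if pooled.** Share = n1 / (n1 + n2). Section 5.7 plans 8 pairs per subject.

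| Source of counts | Share | Part 1 pairs | Part 2 pairs |
|---|---|---|---|
| 10.7 | 5/25 = 20% | 40 | 160 |
| Table 1 | 5/20 = 25% | 40 | 120 |
| Session plan | 3/15 = 20% | 24 | 96 |

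Section 10.7 lets the sponsor stop enrolment early. If Part 1 is already complete by then, the share would be higher.

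**4. Shift of a pooled mean difference.** With equal pairs per subject, shift = share × (Part 1 mean difference − Part 2 mean difference). Each 1 bpm of departure between the parts moves the pooled estimate by 0.20 bpm at a 20% share and 0.25 bpm at 25%. The documents give no value for that departure.

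**5. Size of a selection effect, by simulation under assumed inputs.**

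- Device-minus-reference difference = woman effect + pair error, both normal with mean zero. The SDs (between, within) were (1,2), (2,3), (3,4), (4,3) and (2,6) bpm, with 8 pairs per woman.
- Part 1 and Part 2 sizes were (5,20), (5,15) and (3,12).
- There were K = 1, 2 or 5 equally accurate candidate procedures. The one with the lowest Part 1 mean absolute error was kept. Woman effects were either shared across procedures or independent.
- There were 4,000 runs per setting.

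| Quantity | Result |
|---|---|
| Pooled minus Part 2 only, K = 1 | about 0% |
| Pooled minus Part 2 only, K = 2 to 5 | −1% to −6% (−0.02 to −0.25 bpm) |
| Lower of pooled and Part 2-only, K = 1 | −1% to −3% |
| Sampling SD of the Part 2 estimate | 0.12 to 0.60 bpm |

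The largest selection shift is about half the sampling SD of the Part 2 estimate in the same setting. The third row shows that choosing the analysis set after seeing both results flatters the device slightly even when Part 1 selects nothing.

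**6. Precision given up by excluding Part 1.** Standard error ratio = √(pooled n / Part 2 n): √(25/20) = √(15/12) = 1.118 and √(20/15) = 1.155.

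**The case against.** The strongest reply is that the body of the protocol is clear. Both body sections that address the point, 3.3 and 5.6, exclude Part 1. The only permission is a single sentence in the synopsis, and if 5.6 is followed there are no Part 1 readings to pool. The synopsis also describes the run-in as duplicating the main study, and no document names competing procedures or selection on observed error. Part 1 could be a logistics rehearsal, in which case pooling causes no selection bias. The simulated shifts are small and rest on assumptions, and no hypothesis or threshold depends on them. The access allowed by 10.8.1 is limited to engineering purposes and adds little in an open-label study at a sponsor facility. Section 10.8 names no accuracy statistic at all, so its silence on the analysis set is part of a wider gap.

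Much of this stands. The harm arises only if the pooling sentence is followed, the selection mechanism is assumed, and any numerical effect is probably modest.

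Three parts do not stand. First, Part 1 readings could well exist: 5.7 plans paired scans for every participant, and 6.6 has operators record FHR values on the CRF with no exception for Part 1. Second, the parts are not fully alike. Table 1 allows any operator experience in Part 1 but plans about four novices and one experienced operator in Part 2, and it reserves scanning with fixed parameters for Part 2. Pooling could change the operator mix even if nothing was tuned. Third, a written permission that contradicts three other statements is a conflict between stated rules, and the statistical section is where it should be resolved.

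**Conclusion.** The concern holds as stated and should be fixed. The contradiction is certain and can be read directly from the text. Its consequence is limited: a pooled accuracy set would draw 20% to 25% of its subjects from the run-in that helped settle the procedure.

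The size of any bias cannot be derived from the documents. The 1% to 6% range depends on assumed SDs, an assumed number of candidate procedures and an assumed selection rule, and it falls to about zero if Part 1 selects nothing. In every scenario tried, the shift was below the sampling SD of the Part 2 estimate. Because the study is descriptive, no error rate, power or pass/fail decision changes. What is lost is the independence of the accuracy estimate and a clear statement of whom it describes.

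**What to change.** 1. Delete the pooling sentence from the synopsis Objectives row as it applies to accuracy data.
2. State in the synopsis and in 10.8 that the primary accuracy analysis uses Part 2 subjects only, and keep Part 1 FHR readings out of the accuracy results, in line with 3.3 and 5.6.
3. Record the finalised accuracy procedure and scan parameters in a dated document before the first Part 2 scan.
4. State that adverse events and device issues from both parts are still reported, as 8.8 and 8.10 require, and say whether Part 1 usability data will be used.

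Items 1 and 2 resolve the conflict; items 3 and 4 are small additions that make the separation verifiable. The cost is one sentence removed, two or three added and a short dated record. The analysed set has up to 5 fewer subjects than a pooled one, which makes the standard error about 12% to 15% wider.

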1. BACKGROUND AND JUSTIFICATION

FHR estimation is an important tool for assessment of fetal well-being and development during pregnancy that is traditionally measured using M-mode or Doppler methods on ultrasound systems or with conventional acoustic systems. The Vscan Access R2 Assisted FHR method is an innovative way of assessing FHR that is semi-automated and does not involve any manual measurements once fetal heart is scanned. Assisted FHR method may have clinical benefits, such as improved ease of training and utilization in real clinical cases.

FHR monitoring is important for prenatal care and can be used to indicate a variety of clinically relevant conditions in the mother and fetus, which is the subject of extensive research collaborations worldwide.¹ Training clinicians to perform accurate FHR measurements can be challenging due to various discrepancies in both practice and the acceptable standards for routine FHR measurement.

FHR measurement is important to clinical practice and widely considered safe and effective. A study by Ruma et al.² found that appropriate maternal-fetal care, including FHR determination via obstetric ultrasound improves the outcomes of mothers and their infants, in part due to improved accuracy using advanced ultrasound techniques. This has been demonstrated in large clinical trials, including the Eurofetus study which examined second trimester ultrasounds prospectively.³ American Institute of Ultrasound in Medicine (AIUM) recommends medically necessary fetal ultrasound in the 2nd and 3rd trimester, which are widely considered to be safe for mother and fetus.^{4,5}

The Vscan Access R2 Ultrasound System with its Assisted FHR feature has the potential to improve the accuracy and reproducibility assessment of FHRs for second and third trimester scans, and it also may reduce the variability between clinicians performing similar procedures. Results from this study may be useful for the evaluation of procedural accuracy of the Vscan Access R2 Ultrasound System with Assisted FHR compared to the conventional methods of measuring FHR on ultrasound or Doppler devices.

Justification for Use of GE-Operated Facility

Diagnostic ultrasound device development is an iterative process that involves engineers making changes and adjustments and then evaluating those updates using human subjects. The process listed above is repeated until the product is functioning optimally. One of the key aspects of this process involved the engineer and the device operator viewing images together and discussing the performance of the features and changes under development during the human subject scanning session. In order for this cycle to function both efficiently and economically, it is critical that the human scanning occur in the same location as the Research and Development teams (i.e., onsite at Research Park facility).

The expertise for the product development of the Ultrasound Devices in use under this Study resides at the GEHC Research Park, Wauwatosa, Wisconsin, USA site. In particular, not only the personnel expertise, but certain specialized testing hardware and software to enable development of these Ultrasound Devices, components and accessories are located at the Research Park site.

Facility expertise for product development includes:

- Feasibility; new feature pairings need to be evaluated.
- Verification and Validation; necessary components of the design control cycle.
- Image Quality; the primary determinant of the commercial success of an Ultrasound Device; and determined by a complex matrix of inputs.
- Complaint Resolution; replication of Device complaints in a laboratory controlled setting is an essential part of post-market surveillance.
- Usability testing; to fulfill the requirement for products to have usability testing prior to completion of design output requirements.

- System performance with new hardware and software features.
- Ergonomics and Human Factors; essential part of safe, efficient, and successful product design.

In summary, this study needs to be performed at the Research Park development site because the location contains:

1. Engineering expertise;
2. Clinical domain expertise;
3. User preferences (image quality, presets, knobology) expertise;
4. Competitive benchmarks; and
5. Clinical marketing teams.

1.1 Recommendations for Use of Ultrasound in Research

The World Federation for Ultrasound in Medicine and Biology (WFUMB) includes over 51,155 members in the Regional Federations including the National Societies of Ultrasound in Europe (EFSUMB), in Asia (AFSUMB), in North America (AIUM), in Latin America (FLAUS), in Australasia (ASUM) and in Africa and Mediterranean Countries (MASU).⁴ The study is informed by the WFUMB summary guidance and recommendations for ultrasound examinations for diagnostic purposes as well as for non-diagnostic research and training. Because the exam is performed on a commercially available ultrasound system with exposure not exceeding that normally encountered in clinical practice, the study is considered to pose minimal risk to subjects and adhere to responsible use of ultrasound for research.

1.2 Device Risk and Benefit Analysis

Diagnostic ultrasound devices, components, and accessories are generally considered non-significant risk, and generate images through the use of sound waves rather than ionizing radiation. Diagnostic ultrasound devices share a well-understood safety profile.^{6,7} These devices have been used since the 1950s and are considered one of the safest imaging modalities available with no confirmed adverse biological effects on humans.^{8,9}

This study involves having an ultrasound exam not required for the subject's clinical care. All ultrasound exams done for the study are performed on the the Vscan Access R2 Ultrasound System in a similar manner as routine non-invasive clinical ultrasound exams. Duration and exposure in this study do not exceed those typically encountered in clinical practice and thus involve similar risks as routine clinical ultrasound exams.

Participating in this study does not directly benefit subjects, but will provide images and case data that may benefit others in the future by helping to develop and improve new ultrasound technologies.

1.2.1 Established Safety Measures

In order to minimize the risk of potential adverse biological events, known or unknown, as a result of exposure to ultrasound, the FDA has issued guidelines that require manufacturers of diagnostic Ultrasound devices for 510(k) to limit the acoustic output (energy) of the transducer, the Guidance for Industry and FDA Staff - Information for Manufacturers Seeking Marketing Clearance of Diagnostic Ultrasound Systems and Transducers (2008). These limits, which are displayed on the instrument in the form of a thermal index (TI), both thermal index bone (TIB) and thermal index soft tissue (TIS) and mechanical index (MI), in combination with guidance to the sonographer to limit the scan duration according to the ALARA principle (As Low As Reasonably Achievable) minimizes the risk of a significant adverse biological events.

With these safety measures in place, extensive use of ultrasound in the past 30 years has been shown to be well tolerated in humans.^{6,10} To reduce any potential risks, the duration of Ultrasound scan time in this Study

including the dwell time (i.e. the length of time that the Ultrasound beam is fixed on a specific tissue target), and the acoustic output (TIB, TIC, MI) will be carefully monitored and will be kept within the FDA cleared/approved/recommended levels. All devices used in this study adhere to the limits for thermal index (TI), mechanical index (MI), and other factors set forth by the US Food and Drug Administration (FDA) Guidance for Industry and FDA Staff - Information for Manufacturers Seeking Marketing Clearance of Diagnostic Ultrasound Systems and Transducers (2008), which references the “Standard for real-time display of thermal and mechanical acoustic output indices on diagnostic ultrasound equipment Revision 1,” AIUM/NEMA Standards Publication (AIUM/NEMA 2004a) and IEC 60601-2-37 “Medical electrical equipment - Part 2-37: Particular requirements for the safety of ultrasonic medical diagnostic and monitoring equipment” (IEC 2007). Biological effects of ultrasound are rare within these limits, and ultrasound scanning in this study is thus considered to pose minimal risk of adverse effects in research subjects.

Concern over the bio effects of the acoustic output in vulnerable tissues, such as those of a developing fetus in utero; have been investigated since the 1970s.^{6, 10, 11, 12, 13} To date, obstetric scanning poses minimal risk to mother and fetus if the sonographer abides by the recommended guidelines for scanning obstetric patients set forth in the WFUMB Recommendations on Non-medical Use of Ultrasound (2013).¹⁴

1.3 Controls and Minimization of Bias

The following bias control method will be implemented during the course of this study: selection bias will be limited by consecutively enrolling eligible subjects.

2. DEVICE/PRODUCT DESCRIPTION

2.1 Identity, Mechanism, and Function

Name: Vscan Access R2 Ultrasound with **Assisted Fetal Heart Rate Measurement**

Modality/Type: Ultrasound (U/S)

Manufacturer: GE

Software version: Verified software version cleared for study use

Regulatory Status: Pre-market

Note: A record of number of devices issued, along with applicable identification numbers (e.g. serial/lot/batch) and components/accessories used in this study, will be retained by the Sponsor as part of the clinical history file (CHF), as required by applicable laws and regulations.

The Vscan Access Ultrasound system is a diagnostic ultrasound imaging system manufactured by the study Sponsor, GE Healthcare (GEHC) and equipped with Assisted FHR. It enables visualization and measurement of obstetrical and abdominal anatomical structures and fluid and is intended to be used by qualified and trained primary and specialty health care professionals, including midwives, other paraprofessionals and general physicians. The built-in preset workflows and protocols, particularly enable novice users to scan efficiently and conduct basic screening exams.

The system consists primarily of the core components:

- **Transducer/Probe:** Convert ultrasound waves to electrical signals or vice versa. Vscan Access only supports a convex probe that is part of the Vscan Access device and cannot be detached.
- **Image Quality (IQ) Optimization:** Auto-optimization to image quality for challenging cases.

- Clinical Software tools: Software features like ScanCoach, Clinical protocols, touch screen user interface, patient education videos to enhance clinical efficacy and workflow.
- Applications: Imaging and analysis for OB and Abdominal applications

Routine commercially available ultrasound accessories and components (lubricating gels) may be used during study procedures at the discretion of the study staff. The device will be used for research purposes in this study in accordance with applicable sections of US FDA 21 CFR and other applicable laws and regulations. This study uses the device with a software that is verified but is yet to be commercially available.

Vscan Access Ultrasound system is CE marked to meet CE marked to European Medical Devices Directive (MDD) 93/42/EEC. Vscan Access is not available in the USA.

The Vscan Access Ultrasound System and its accessories and components under study are considered Class II in the United States per 21 CFR §892.1550 (Ultrasonic pulsed-Doppler imaging system), 21 CFR §892.1560 (Ultrasonic pulsed echo imaging system), and 21 CFR §892.1570 (Diagnostic ultrasonic transducer).

The results of this study are intended for future use in clinical engineering and development next generation ultrasound technologies and de-identified information may be in the United States and other countries.

